5.3.2 Clinical Data Summary

To date, 7 clinical studies have been completed, consisting of 6 Phase I clinical studies (SLx-2119-09-01, KD025-101, KD025-102, KD025-103, KD025-105, and KD025-106) in healthy subjects, and 1 Phase IIa study (KD025-205) in subjects with psoriasis vulgaris. Additionally, a Phase II study (KD025-206) in subjects with psoriasis vulgaris has been clinically completed; however, the clinical study report is pending. In addition to the completed studies, 5 Phase II studies are ongoing in subjects with chronic graft versus host disease (cGVHD) (KD025-208 and KD025-213), IPF (KD025-207), psoriasis (KD025-211) and systemic sclerosis (KD025-209). A drug-drug interaction phase 1 study is currently ongoing (KD025-107).

KD025 was generally well-tolerated, with most adverse events (AEs) considered mild or moderate in severity and a low incidence of serious adverse events (SAEs) overall. An increase in liver function test AEs at the highest dose tested in Phase 2 studies (400 mg twice daily [BID]) (Study KD025-206) led to this dose no longer being used in subsequent studies.

The most common ($\geq 5\%$ overall) AEs were alanine aminotransferase (ALT) increased (10.8%), nausea (9.7%), diarrhoea (8.9%), upper respiratory tract infection (8.9%), fatigue (7.8%), aspartate aminotransferase (AST) increased (7.8%), gamma-glutamyltransferase increased (7.8%), headache (6.3%), cough (6.3%), and dyspnoea (5.2%).

The most common AEs were generally also the most common treatment related AEs. The majority of these events were mild to moderate in severity.

To date no clinically significant AEs suggestive of photo-toxicity have been reported in KD025 studies. All but one of the skin and subcutaneous tissues system organ class (SOC) events reported to date have been mild to moderate in severity (the exception being a Grade 3 "rash erythematous" likely related to progression of cGVHD). Of note, most of the subjects treated with KD025 have been enrolled into studies of psoriasis and GVHD.

No treatment related deaths have occurred to date.

The identified and potential risks noted in association with KD025, detailed in the IB [12], are balanced by the anticipated benefits that may be afforded to subjects with psoriasis vulgaris, IPF and cGVHD.

6 Rationale

6.1 Study Rationale

This study is being conducted to investigate the oral pharmacokinetics (PK), intravenous (IV) PK, mass balance recovery and metabolite profiling and identification of ^{14}C -KD025.

Kadmon Pharmaceuticals LLC. is developing KD025, a ROCK2 selective inhibitor, for the treatment of autoimmune diseases.

Part 1

Knowing the absolute bioavailability of an oral drug product is a regulatory requirement in some regions, eg Australia. In addition, understanding the bioavailability of a drug and the factors that influence absorption, may guide the formulation development strategy. The IV microtracer technique is an established methodology for measuring the IV and oral kinetics of a drug in the same individuals in a single dosing period. The technique involves concurrent administration of a microdose of the drug containing microtracer amounts of ^{14}C with a single oral therapeutic dose, which avoids the concerns of dose-dependent kinetics when extrapolating IV PK from a microdose, as the systemic exposure is at therapeutic concentrations. This design enables measurement of ^{14}C -labelled drug in the plasma following IV dosing via sensitive accelerator mass spectrometry (AMS) techniques, and measurement of the unlabelled parent in the plasma by standard high performance liquid chromatography mass spectrometry/mass spectrometry (HPLC MS/MS) techniques. Thus, it is possible to obtain the IV PK parameters with the associated variability, and calculate the absolute bioavailability. In

addition, because the IV dose administration involves giving a low volume of a low concentration of parent drug, an advantage of this approach is that it is much easier to develop an IV formulation for microdosing than it would be for a higher clinical dose.

Part 2

The current study is designed to collect samples and to generate data for the absorption, distribution, metabolism and elimination (ADME) of KD025 in humans, as well as generating samples for metabolite profiling and structural identification.

6.2 Dose Rationale

Part 1

KD025 in doses ranging from 20 to 1000 mg once daily (QD) to 500 mg BID have generally been well tolerated. A single oral dose of 200 mg of KD025 followed by an 100 µg IV dose of [¹⁴C]-KD025, given 1.75 h after the oral dose has been administered (estimated to end at the time of maximum plasma concentration [T_{max}] for the oral dose [2 h]), has been selected for Part 2 of this study. The 200 mg dose has been well tolerated as a single dose and in repeat dosing in healthy subjects and patients with psoriasis and cGVHD; repeat dosing at 400 mg QD has been well tolerated in patients with cGVHD and IPF. The 200 mg dose provides a clear PK profile, in the linear range, well above the lower limit of quantification, and is in the expected therapeutic range.

Part 1 is the absolute bioavailability part of the study where an IV micro dose of KD025 containing microtracer amounts of ¹⁴C is administered following administration of an oral dose of KD025 to determine the bioavailability of the oral dose compared with the IV dose. According to the International Council for Harmonisation (ICH) M3 guidance, a micro dose is a dose that is <1/100th of the pharmacologically active dose up to a maximum of 100 µg. In addition, to ensure that the IV micro dose does not contribute significantly to the exposure following oral dosing, the IV dose is reduced further and in this study will be 1/1000th of the oral dose.

An IV microtracer dose is one that contains not more than (NMT) 37.0 kBq (1000 nCi). This has been selected as it is the standard radioactive dose used in this type of study and will be sufficient to meet the objectives of Part 1, but contains a low enough amount of radioactivity so as not to cause a significant risk to the subjects.

Therefore the IV dose for this study will be 100 µg [¹⁴C]-KD025 containing NMT 37.0 kBq (1000 nCi). This IV dose is 1/2000th of the oral dose administered in this study and <1/100th of the likely therapeutic dose, and hence is an appropriate 'IV microtracer dose'.

Part 2

KD025 in doses ranging from 20 to 1000 mg QD to 500 mg BID have generally been well tolerated. A single dose of 200 mg [¹⁴C]-KD025 has been selected for Part 2 of this study. The 200 mg dose has been well tolerated as a single dose and in repeat dosing in healthy subjects and patients with psoriasis and cGVHD; repeat dosing at 400 mg QD has been well tolerated in patients with cGVHD and IPF. The 200 mg dose provides a clear PK profile, in the linear range, well above the lower limit of quantification, and is in the expected therapeutic range.

The dose of radioactivity for Part 2 has been determined following review of human dosimetry calculations provided by Public Health England (PHE). In accordance with the 'as low as reasonably practical' principle, the lowest amount of radioactivity will be administered that gives confidence that the study objectives will be met. Based on the human dosimetry calculations, a radioactive dose of no more than 9.8 MBq (215 µCi) by the oral route will be necessary. Adequate metabolite profiling of some key plasma samples may not be possible at a radioactive dose less than this.

Subjects will be participating in both study Parts 1 and 2, therefore the radioactive dose for Part 2 will be adjusted to take into account the microtracer amount of radioactivity that the subjects will receive in Part 1 of the study (37 kBq/1000 nCi). Thus the oral dose for Part 2 will have a radioactive dose containing NMT 9.8 MBq (215 µCi). The total committed effective dose subjects will receive is 3 mSv, falling within International Commission on Radiological Protection (1992) Guidelines for Category IIb studies (1 to 10 mSv).

To ensure that the [¹⁴C] drug products do not exceed the limit for radioactive dose approved by the Administration of Radioactive Substances Advisory Committee (ARSAC), the target specific activity of the [¹⁴C] drug substance will be set at 90% of 90% of the threshold radioactive dosing limit. This will ensure provision for a ± 10% range on the [¹⁴C] drug substance specification for specific activity and a ± 10% range on the [¹⁴C] drug substance assay in the drug product, thereby providing continued assurance for compliance with the ARSAC-approved limit for drug product radioactivity dose.

A positive food effect has been reported in previous studies and current dosing instructions in on-going Phase 2 studies recommend administration of KD025 with food [12]. Therefore oral administration of KD025 in this study will be performed in the fed state, to ensure characterisation of absorption, metabolism and excretion in conditions that best mimic intended clinical use.

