5.2 Investigational Medicinal Product(s)

The following investigational medicinal products (IMPs) will be used in this clinical study (Table 1).

Table 1 Investigational Medicinal Products

Part	Investigational Medicinal Product	Dose and Route of Administration
1	KD025 Tablet, 200 mg	200 mg (as 1 x 200 mg tablet), Oral
	[¹⁴ C]-KD025 solution for infusion, 20 µg/mL	100 µg, containing NMT 37 kBq (1000 nCi), IV infusion
2	[¹⁴ C]-KD025 capsule, 200 mg	200 mg, containing NMT 9.8 MBq (215 µCi) ¹⁴ C, Oral

¹⁴C = carbon-14, IV = intravenous, kBq = kilobecquerel, MBq: megabecquerel µCi: microcurie, nCi = nanocurie, NMT = not more than. All IMPs are described as free base equivalent.

Only subjects enrolled in the study may receive study treatment and only authorised site staff may supply or administer study treatment. All study treatments will be stored in a secure, environmentally-controlled, and monitored (manual or automated) area in accordance with the labelled storage conditions. Access will be limited to the investigator and authorised site staff.

Where Quotient Sciences is manufacturing the IMP(s), suitability of the manufacturing process will be documented in a Pharmaceutical Development and Control Strategy Report.

All IMPs will be reconciled and destroyed in accordance with the study-specific quality agreement and technical addendum.

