6.4.2 Risks associated with Radiation Exposure

The [¹⁴C]-KD025 solution for infusion and [¹⁴C]-KD025 capsule will contain a radionuclide (NMT 9.8 MBq [267 µCi]) so subjects will be exposed to ionising radiation. The effective dose that each subject will receive from one administration will not exceed 3 mSv. This is approximately 1 year and 1 month of the average radiation exposure received in the UK each year (2.7 mSv). It is believed that any increase in the amount of radiation that is received above natural radiation carries a risk of later developing serious and possibly fatal conditions. The risk associated with the maximum possible dose of radiation in this study is very small indeed and is considered to be acceptable.

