Part 2 is an open-label, non-randomised ADME assessment in 6 healthy male subjects. Following a minimum washout period of 7 days, subjects who participated in Part 1 of the study will be admitted to the clinical unit for participation in Part 2 of the study. On Day 1 each subject will receive a single oral administration of 200 mg [¹⁴C]-KD025 capsule containing (NMT 9.8 MBq) (215 µCi) [¹⁴C] (Treatment C) on the morning of Day 1 after a standard breakfast.

Treatment	IMP Dose
C	[¹⁴ C]-KD025 capsule, containing NMT 9.8 MBq (215 µCi) ¹⁴ C, 200 mg

¹⁴C:carbon-14, MBq: megabecquerel, µCi: Microcurie, NMT: not more than. IMP is described as free base equivalent.

Details of IMPs can be found in Section 5.2

A subject in Part 2 will be considered evaluable if they have provided biological samples for up to 168 h after drug administration or have demonstrated >90% mass balance recovery, or have <1% of the administered dose eliminated in excreta for two consecutive days, whichever is the sooner.

[figure not shown]
Approximately 7 days after subjects have been discharged from Part 1 of the study, subjects will be admitted to the clinical unit on the evening of the day prior to IMP administration (Day -1) for the confirmation of eligibility and baseline procedures. Subjects will be dosed on the morning following admission (Day 1). Following an overnight fast (approximately 10 h), subjects will consume a standard breakfast and will receive a single dose of [¹⁴C]-KD025 capsule (Treatment C) 30 min after the start of breakfast. Subjects will remain resident in the clinic until up to 168 h after dosing (up to Day 8). It is planned that subjects will be released as a group when all subjects have achieved a mass balance cumulative recovery of >90% or if <1% of the dose administered has been collected in urine and faeces within 2 separate, consecutive 24 h periods. This may result in the subjects being discharged as a group prior to completion of the planned residency period. Once the discharge criteria or the planned residency period has been achieved, the subjects will undergo discharge assessments and collection of all samples (blood, urine and faeces) will be stopped.

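### The Part 2 oral radioactivity cap is printed nine times as 9.8 MBq (215 µCi), but 9.8 MBq is 265 µCi: the two limits differ by 23%, and 215 µCi is probably the wrong one

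*Protocol*

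**What the plan says.** Protocol Section 6.2 sets the limit for the Part 2 capsule: "a radioactive dose of no more than 9.8 MBq (215 µCi) by the oral route will be necessary". The same pair of figures stands at nine places:

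- Protocol synopsis, three times: the Part 2 methodology text, the Treatment C table, and the table of investigational products.
- Protocol Section 5.2, Table 1: "containing NMT 9.8 MBq (215 µCi".
- Protocol Section 6.2, Part 2, twice.
- Protocol Section 8.1.2, twice. The text reads "capsule containing (NMT 9.8 MBq) (215 µCi", and the treatment table repeats the pair.
- SAP Section 5.1.2, once, in the same form as the Section 8.1.2 text.

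A tenth mention of the limit, in Protocol Section 6.4.2, keeps the MBq figure but gives a different µCi figure: "capsule will contain a radionuclide (NMT 9.8 MBq [267 µCi]) so subjects will be exposed to ionising radiation".

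Three other statements bear on the point.

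- **Conversion.** The Part 1 dose rationale in Section 6.2 gives both units for the infusion: "An IV microtracer dose is one that contains not more than (NMT) 37.0 kBq (1000 nCi".
- **Effective dose.** Section 6.2 says "The total committed effective dose subjects will receive is 3 mSv". Section 6.4.2 says "The effective dose that each subject will receive from one administration will not exceed 3 mSv".
- **Drug-substance target.** Section 6.2 says the target specific activity "will be set at 90% of 90% of the threshold radioactive dosing limit", to allow for two ±10% ranges while staying within the limit approved by ARSAC.

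**The concern.** A limit printed in two units should be one limit. Here the two figures describe different amounts of radioactivity. A capsule between 7.955 and 9.8 MBq satisfies one and exceeds the other. This is not background text: it is the operative upper limit on radioactivity given to healthy volunteers, and it appears in the product table and in the treatment definition.

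The ambiguity matters in both directions. If 215 µCi were the intended limit, the MBq figure would allow 23% too much. If 9.8 MBq is the intended limit, someone working in µCi would hold the dose about 19% too low. Section 6.2 itself warns that less radioactivity than the stated dose may not support metabolite profiling of some key plasma samples.

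**Working it through.** **Conversion factor, from the protocol's own pair.** Section 6.2, Part 1, equates 37.0 kBq with 1000 nCi. Since 1000 nCi = 1 µCi, 1 µCi = 0.037 MBq. The Part 1 pair is internally exact.

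**Attempt to reproduce 215 µCi from 9.8 MBq.**

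| Step | Calculation | Result |
|---|---|---|
| Direct conversion | 9.8 / 0.037 | 264.9 µCi |
| Lowest value that rounds to 9.8 | 9.75 / 0.037 | 263.5 µCi |
| Highest value that rounds to 9.8 | 9.85 / 0.037 | 266.2 µCi |
| Less the Part 1 infusion | (9.8 − 0.037) / 0.037 | 263.9 µCi |
| Plus the Part 1 infusion | (9.8 + 0.037) / 0.037 | 265.9 µCi |

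None of these gives 215. Neither rounding nor the allowance for the Part 1 dose explains the figure.

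**Reverse conversion.** 215 × 0.037 = 7.955 MBq.

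**Size of the disagreement.** 264.86 / 215 = 1.232, so 9.8 MBq is 23.2% above 215 µCi. In the other direction, 7.955 / 9.8 = 0.812, so 215 µCi is 18.8% below 9.8 MBq.

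**Which figure is wrong.**

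- The MBq value is 9.8 at all ten mentions. Only the µCi value varies: 215 nine times, 267 once.
- 267 × 0.037 = 9.879 MBq, and 9.879 / 9.8 = 1.008. The Section 6.4.2 figure is therefore within 0.8% of 9.8 MBq.
- The target rule is 0.9 × 0.9 = 0.81 of the limit. Applied to 9.8 MBq it gives 0.81 × 9.8 = 7.938 MBq, and 7.938 / 0.037 = 214.5 µCi. So 215 µCi coincides with the drug-substance target for a 9.8 MBq limit. The documents do not say that it came from there.

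**The 267 µCi figure.** It lies just outside the capsule-only range of 263.5 to 266.2 µCi. Adding the 1 µCi infusion moves the range to 264.5 to 267.2 µCi, which contains it. The Section 6.4.2 sentence names both the infusion and the capsule, so 267 may be a two-dose total, or it may be a small error. The text does not say which.

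**The 3 mSv figure.** 3 / 9.8 = 0.306 mSv per MBq; 3 / 7.955 = 0.377 mSv per MBq. No dose coefficient is given, so neither value can be checked.

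**The case against.** The strongest reply is that this is a wrong secondary-unit conversion beside a primary-unit limit that never varies, and that nothing in the trial's results depends on it. Section 6.2 ties the drug-substance target to the ARSAC-approved limit, not to the figure in brackets. Section 18.4 requires a Public Health England dosimetry report in the ARSAC application, ARSAC approval before dosing, and the ARSAC practitioner's approval of the final protocol. SAP Section 9.3.2 divides by the actual radioactive dose, so recovery is unaffected. All of this stands, and it limits the consequence. It does not make the printed limit correct.

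A reader might also infer more than the documents support:

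- **That 3 mSv confirms 9.8 MBq.** In Section 6.2 the 3 mSv statement follows a sentence that prints both 9.8 MBq and 215 µCi. Without a coefficient it fits either figure.
- **That the exposure table would display a breach.** SAP Section 10.1 summarises the Part 2 dose in MBq and µCi, but the shell of Table 14.1.5.2 prints no cap and the SAP plans no comparison with one. The conflict would be seen only by going back to the design text.
- **That capsules could exceed the limit by about 21%.** Taking the two ±10% ranges as multiplicative, product made to 9.8 MBq could reach 0.81 × 1.21 × 9.8 = 9.605 MBq, or 259.6 µCi, and 259.6 / 215 = 1.207. This requires one reading to be used for manufacture and the other for the limit, and nothing in the documents says anyone would do that. On a single reading the maximum is 0.81 × 1.21 = 98.01% of the limit.

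**Conclusion.** The concern holds. The cap is wrong as written: 9.8 MBq and 215 µCi cannot both be the limit, and they differ by 23%. This part rests only on the conversion that the protocol itself uses. Repetition at nine places in two documents rules out a text-extraction fault.

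That 215 µCi is the wrong figure is probable, not established. It rests on the constancy of 9.8 MBq and on the near-match in Section 6.4.2. The agreement with 81% of the limit offers a plausible origin, but that is inference. The deciding documents, the dosimetry report and the ARSAC approval, are not available here.

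It does not follow that any volunteer would receive more than the approved radioactivity, because the approved figure is not stated outside these conflicting pairs. Nor does any endpoint change. The point should be corrected because it is a dose limit, not because it threatens the analysis.

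**What to change.** 1. Confirm the limit against the Public Health England dosimetry report and the ARSAC approval.
2. State one cap with matching units at all nine places in the protocol and SAP: NMT 9.8 MBq (265 µCi) if 9.8 MBq is confirmed.
3. In Section 6.4.2, correct 267 µCi to the capsule's equivalent, or label it as the total for infusion plus capsule (9.837 MBq, about 266 µCi) if that is what is meant.

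The cost is one check against two existing documents and a text correction. Section 17.1 routes amendments about the administration of radioactive substances through the ARSAC practitioner before any submission to ARSAC, so that review may also be needed. No subjects, procedures or analyses are added.

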6.3 Population Rationale

The European Medicines Agency (EMA) propose to include subjects in the age group 18 to 55 years with normal weight who are non-smokers without a history of alcohol or drug abuse. The latter criteria are proposed to avoid interaction on drug metabolism and to avoid non-compliance. In order to avoid any interaction with other medication, no co-medication except 4 g of paracetamol per day (within 24 h) will be allowed.

We acknowledge the ARSAC Notes for Guidance recommend that wherever possible, healthy subjects selected for research projects should be aged over 50 years [13]. However, Part 2 of this study is designed to generate data for supporting the investigation of the human ADME of a drug, as well as generating samples for metabolite profiling and structural identification.

There are 2 main reasons for generating these data within a clinical development programme. The first is to provide human metabolite data that can be used to interpret the metabolism profiles seen in the preclinical species employed in the longer term toxicity studies, to ensure that there is adequate toxicology coverage for the safe development of the drug in patients. The second is to provide data to understand how the drug is processed in physiologically normal subjects, because understanding the routes of metabolism and elimination in a healthy population generates the appropriate data to guide the clinical pharmacology package required to fulfil the regulatory requirements of a New Drug Application (NDA).

In order to address these 2 main aims of an ADME study, investigation of the drug under development is required in a population with normal physiological function, as it is recognised that certain physiological processes eg renal function, deteriorate with age and therefore it is preferable to use as healthy as possible population, to mitigate against factors which may make interpretation of the data difficult. Also, healthy subjects as a trial population are ideal since they have a relatively stable physiological, biochemical and hormonal status, which removes any disease-related variations and variations due to concomitant medications. Therefore given the aims of this ADME study our target age range for this study will be 30 to 65 years.

Formal rat and rabbit embryo-foetal developmental toxicology studies with KD025 demonstrated potential for embryo-foetal toxicity and/or malformations at clinically relevant exposures. Therefore subjects with pregnant partners will be excluded from this study.

The purpose of this study is to investigate the oral pharmacokinetics (PK), intravenous (IV) PK, mass balance recovery and metabolite profiling and identification of ¹⁴C-KD025. It is therefore an advantage to enrol a relatively homogeneous population and to minimise variability. Based on the above considerations and target population, healthy male subjects, aged 30 to 65 years are considered suitable for this study.

